5.7.3. Exploratory Endpoints

5.7.3.1. Biomarkers Related to TGF- β

Biomarkers GDF8, GDF11, and GDF15 will be presented in listing only.

5.7.3.2. FACT-An Questionnaire

The FACT-An Questionnaire will be completed at Screening and Cycle 5 Day 1 or End of Treatment (for patients who withdraw early) visits for the Expansion Cohort only. The Fact-An questionnaire contains 47 questions which are divided into the following sub scales:

- Physical Well-Being (PWB) (7 questions: Item Score range 0 - 28)
- Social/Family Well-Being (SWB) (7 questions: Item Score range 0 - 28)
- Emotional Well-Being (EWB) (6 questions: Item Score range 0 - 24)
- Functional Well-Being (FWB) (7 questions: Item Score range 0 - 28)
- Anemia subscale (AnS) (20 questions: Item Score range 0 - 80)

Patients give individual responses to each question on a scale of 0 to 4 (0=Not at all; 1=A little bit; 2=Slightly; 3=Quite a bit; 4=Very much). Item scores in the PWB and EWB sub scales will be derived by subtracting the response value from 4. Similarly, all Item Scores in the AnS subscale except Item Codes An5, An7, BL4 and An13³ will be derived by subtracting the response value from 4. Thus, a higher Item Scores indicates a better quality of life.

Subscale totals will be derived as follows:

$$\frac{\text{Sum of Item Scores} \times \text{Number of Items in Subscale}}{\text{Number of Items Answered}}$$

For example, if 6 questions are answered in the Physical Well-Being subscale and the Item scores sum to a total score 18 the subscale score will be $(18 \times 7)/6 = 21$.

If 50% or more of responses in any subscale are missing the subscale total will be set to missing.

The following total scores will also be derived:

FACT-An Total Outcome Index (TOI) derived as: PWB + FWB + AnS (Score range 0 – 136)

FACT-G Total Score (FACT-G) derived as: PWB + SWB + EWB + FWB (Score range 0 – 108)

FACT-An Total Score (FACT-An) derived as: PWB + SWB + EWB + FWB + AnS (Score range 0 – 188)

If 20% or more of the responses that contribute to the FACT-G score are missing the FACT-G score will be set to missing (i.e. at least 22 of the 27 items contributing to FACT-G must be present). Furthermore, FACT-An TOI, FACT-G and FACT-An scores should only be calculated if all component subscales have valid scores. If any subscale total is missing the respective total scores to which the subscale contributes will also be set to missing. A higher FACT total score indicates a better quality of life.

Individual subscale scores and total scores will be summarized by visit. All derived subscale and total scores and all individual responses will be listed.

The association between FACT-An improvement and RBC-TI response will also be explored.

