3.1. Study Design

Patients who meet the study eligibility criteria will be enrolled within 28 days of screening. Patients in all cohorts will receive luspatercept, administered subcutaneously (SC), every 3 weeks for up to 5 cycles. Dose delay(s) and dose reduction(s) may be required for individual patients as outlined in protocol Section 10.8.1, Patient Dose Modification Rules.

Each dose escalation cohort will consist of a minimum of 3 patients. The dose level of luspatercept for the first cohort will be 0.125 mg/kg and the dose level(s) for subsequent cohort(s) will follow a modified Fibonacci dose escalation scheme with a maximum dose level of 0.25 mg/kg for cohort 2, 0.50 mg/kg for cohort 3, 0.75 mg/kg for cohort 4, 1.0 mg/kg for cohort 5, 1.33 mg/kg for cohort 6, 1.75 mg/kg for cohort 7, and a maximum dose level not to exceed 1.75 mg/kg. Once a minimum of 3 patients in a cohort have completed Study Day 29, the Safety Review Team (SRT) will review preliminary safety and hematologic response data and make recommendations to the Sponsor regarding whether or not to enroll an additional 3 patients in that cohort, enroll a new cohort at a higher or lower dose, or proceed to the expansion cohort.

Expansion cohort 1 (n= approximately 30) will be treated with ACE-536 at a starting dose level of 1.0 mg/kg. Expansion cohort 1 will consist of a minimum of 10 patients who are high transfusion burden (HTB) patients and 10 patients who are low transfusion burden (LTB) patients, if feasible.

Expansion cohort 2 will be treated with ACE-536 at a starting dose level of 1.0 mg/kg. Expansion cohort 2 will be divided into two groups designated expansion cohort 2A and 2B. The targeted accrual for each group will be 25 eligible and evaluable patients but permitted to range from 22 to 28 for administrative reasons. The maximum number of patients treated will be 56.

- Expansion cohort 2A: LTB patients with $\geq 15\%$ ring sideroblasts in the bone marrow (RS+), less than 4 weeks of exposure to erythropoietin stimulating agents (ESAs), and serum erythropoietin (EPO) level ≤ 200 U/L at screening.
- Expansion cohort 2B: Patients with $< 15\%$ ring sideroblasts in the bone marrow (RS-) and ≤ 6 RBC units in 8 weeks prior to cycle 1 day 1 (C1D1). This group will consist of a minimum of 10 patients who have less than 4 weeks of exposure to ESAs and 5 patients who have received ≥ 4 weeks of treatment with ESAs.

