5. STATISTICAL METHODOLOGY

5.1. Definitions

Low Transfusion Burden (LTB)

LTB patients are defined as those who received < 4 units of RBCs within 8 weeks prior to Cycle 1 Day 1.

High Transfusion Burden (HTB)

HTB patients are defined as those who required ≥ 4 units of RBCs within 8 weeks prior to Cycle 1 Day 1.

Baseline Hemoglobin

Baseline hemoglobin will be an average of hemoglobin measurements within 28 days of Cycle 1 Day 1, excluding measurements within 7 days following RBC transfusion.

Baseline Transfusion Burden

Baseline transfusion burden will be calculated as the total amount of RBC transfusion during the 8 weeks prior to Cycle 1 day 1.

Baseline for Other Parameters

Baseline erythropoietin (EPO) is defined as the maximum test value within 28 days of Cycle 1 Day 1. For all other parameters, baseline is defined as the last observation on or prior to Cycle 1 Day 1.

End of Treatment (EOT)

Procedures and evaluations for the end of treatment visit should be performed on Day 113 (± 7 days) (28 days after the last dose of ACE-536).

Post Treatment Follow-Up (PTFU)

Procedures and evaluations for the post treatment follow-up visit should be performed on Day 141 (± 7 days) (28 days after EOT visit).

End of Study (EOS)

Procedures and evaluations for the end of study visit should be performed on Day 169 (± 7 days) (56 days after the Day 113/EOT visit).

Patients who discontinue treatment early should complete the end of treatment visit at the time of discontinuation and complete the post-treatment follow-up (PTFU) and EOS follow-up visits 28 days (± 7 days) and 56 days (± 7 days) after the EOT visit.

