5.7.2. Secondary Efficacy Endpoints

5.7.2.1. RBC Transfusion Independence

For patients with ≥ 2 units of RBC transfusion at baseline, RBC transfusion independence (RBC-TI) response is defined as not requiring RBC transfusion for more than 8 weeks while on treatment.

The proportion of RBC-TI responders will be estimated by a point estimate along with the exact 95% confidence interval based on binomial distribution. The denominator is the number of patients with ≥ 2 units of RBC transfusion at baseline.

Time to RBC-TI will be defined the time from the first dose date to the starting date of the first consecutive 8-week window not requiring RBC transfusion. Duration of RBC-TI will be

calculated as the longest period of time not requiring RBC transfusion during treatment and will be censored at the last record date for ongoing responses.

Both time to and duration of RBC-TI will be analyzed as continuous variables and summarized by descriptive statistics for RBC-TI responders only. Duration of RBC-TI will also be analyzed as a time to event variable using Kaplan-Meier method.

The derivations of RBC-TI response, time to and duration of RBC-TI will be listed for each patient.

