¹² **End of Treatment (EOT):** Should be performed 28 days (\pm 7 days) after the last dose of ACE-536. Patients who discontinue treatment early should complete the end of treatment visit at the time of discontinuation and complete the post-treatment follow-up (PTFU) and EOS follow-up visits 28 days (\pm 7 days) and 56 days (\pm 7 days) after the EOT visit.

¹³ **End of Study (EOS):** Should be performed 56 days (\pm 7 days) after the Day 113/EOT visit.

¹⁴ **Day 85 \pm 2 days** is the last possible study day that ACE-536 may be administered, regardless of the cycle.

¹⁵ If a **dose delay** is required per the dose modification rules the patient will not be dosed. The patient will return weekly to assess hematology results and adverse events until the patient is eligible to administer the next dose of ACE-536. The patient should resume the study at the planned dosing cycle (e.g. if the patient missed a dose at C4D1, then they would resume dosing at C4D1 and not skip to C5D1). Note: study days may vary if a dose delay occurred during the treatment period.

¹⁶ If the patient has a **positive ADA** result at their last assessment, the patient may be asked to return approximately every three months for additional testing, until a negative result is obtained or the result is considered stabilized.

¹⁷ For the **first dose of ACE-536**, dosing should occur after a minimum of 7 days post-transfusion and a minimum of 24 hours prior to a scheduled transfusion.

¹⁸ **Expansion cohorts** only, administration of quality of life questionnaires. Quality of life questionnaire not required for expansion cohort 2 or 3 patients at C5D1.

¹⁹ **Quality of life questionnaires** should be completed at the EOT visit for patients that discontinue treatment early and for all expansion cohort 2 and 3 patients.

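### FACT-An is summarised only as observed scores at visits that hold different patients, and its undefined improvement is related only to RBC transfusion independence

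*SAP*

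**What the plan says.** FACT-An is an exploratory endpoint in the expansion cohorts. SAP section 5.7.3.2 sets out the scoring in detail and then gives two analyses. The first is "Individual subscale scores and total scores will be summarized by visit". The second is "The association between FACT-An improvement and RBC-TI response will also be explored". Scores and individual responses are also listed. The section has no change from screening, paired count or completion rate, and no statement of what counts as improvement.

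On timing, section 5.7.3.2 states: "The FACT-An Questionnaire will be completed at Screening and Cycle 5 Day 1 or End of Treatment (for patients who withdraw early) visits". Footnote 19 of the schedule in SAP Appendix 2 says that the questionnaires "should be completed at the EOT visit for patients that discontinue treatment early and for all expansion cohort 2 and 3 patients", and footnote 18 drops the Cycle 5 Day 1 form for cohorts 2 and 3. Protocol section 12.6 adds a form at End of Study for the expansion cohorts, which section 5.7.3.2 does not mention.

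On response, SAP section 5.7.2.1 restricts RBC transfusion independence (RBC-TI) to transfused patients: "The denominator is the number of patients with ≥ 2 units of RBC transfusion at baseline". Low transfusion burden is a wider class (SAP section 5.1): "LTB patients are defined as those who received < 4 units of RBCs within 8 weeks prior to Cycle 1 Day 1". One cohort consists only of such patients (SAP section 3.1): "Expansion cohort 2A: LTB patients with" at least 15% ring sideroblasts.

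For iron, erythropoietin, bone and hemolysis parameters (SAP sections 5.7.2.5 to 5.7.2.8), laboratory values (5.8.3) and vital signs (5.8.4), the SAP does plan change from baseline. Missing forms are not imputed (5.2 and 5.14.1).

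**The concern.** The trial has no control arm, so the most direct evidence on quality of life is how each patient's score moves from that patient's own screening value. A table of means by visit answers that question only if the same patients stand in each row. Here the schedule assigns different patients to different rows, so a reader who compares rows may take a change in who is counted for a change in how patients feel.

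The response link has a separate gap. FACT-An contains an anemia subscale, and for low-burden patients the SAP judges erythroid response by hemoglobin (sections 5.7.1 and 5.7.2.2). Yet the only response variable named for the association is one that some of these patients cannot have. Because improvement is undefined, the score, visit and threshold would all be chosen after open-label data have accumulated.

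**Working it through.** **Scoring arithmetic in section 5.7.3.2.** No sample size, power or effect figure is involved. The section's own figures reproduce:
- Proration example: (18 × 7)/6 = 21.
- TOI maximum: 28 + 28 + 80 = 136.
- FACT-G maximum: 28 + 28 + 24 + 28 = 108.
- FACT-An maximum: 108 + 80 = 188.
- FACT-G completeness: 20% of 27 items is 5.4, so 6 missing items void the score and at least 22 are needed.

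**Who stands in each row of a by-visit table** (SAP 5.7.3.2, Appendix 2 footnotes 18 and 19, Protocol 12.6):

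| Visit | Cohort 1 | Cohorts 2 and 3 |
|---|---|---|
| Screening | all with a form | all with a form |
| Cycle 5 Day 1 | those still on treatment | not required |
| End of Treatment | early discontinuers only | all, including early discontinuers |
| End of Study | those still in the study | those still in the study |

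Within cohort 1, the Cycle 5 Day 1 and End of Treatment rows hold different patients even if every form is returned. If the expansion cohorts are pooled, the Cycle 5 Day 1 row is cohort 1 alone, and the End of Treatment row is cohort 1 early discontinuers plus cohorts 2 and 3. Within cohorts 2 and 3 taken separately, Screening and End of Treatment cover the same patients except for missing forms.

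**Size of the shift in cohort 1, with no change in any patient.** Let d be the share stopping before Cycle 5 Day 1, and D the amount by which their screening mean lies below that of the others. Then:
- Cycle 5 Day 1 mean minus screening mean = d × D.
- End of Treatment mean minus screening mean = −(1 − d) × D.
- Paired change, each patient against their own screening score = 0.

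The documents give neither d nor D, so these are assumptions. Take n = 30 (the planned cohort 1 size), 6 early discontinuers (d = 0.20), D = 10 and a screening mean of 120 in the others:
- Screening mean = (24 × 120 + 6 × 110)/30 = 118.
- Cycle 5 Day 1 mean = 120, a shift of +2 (0.20 × 10).
- End of Treatment mean = 110, a shift of −8 (−0.80 × 10).

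Range at Cycle 5 Day 1:

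| Share stopping | D = 10 | D = 20 | D = 30 |
|---|---|---|---|
| 10% (3 of 30) | 1 | 2 | 3 |
| 20% (6 of 30) | 2 | 4 | 6 |
| 30% (9 of 30) | 3 | 6 | 9 |

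If early discontinuers score higher at screening, D is negative and every sign reverses. The documents do not settle the sign.

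**Who has a response value for the association:**

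| Baseline units in 8 weeks | Class | RBC-TI | mHI-E and HI-E |
|---|---|---|---|
| 0-1 | low burden | not defined | defined (hemoglobin) |
| 2-3 | low burden | defined | defined (hemoglobin) |
| 4 or more | high burden | defined | defined (transfusion) |

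Only the first row is lost. Cohort 2A (22 to 28 planned) is all low burden, and cohorts 1, 2B and 3 can also contain such patients. The split between 0-1 and 2-3 units is not given, so within cohort 2A the loss could be anything from none to all 28.

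**The case against.** The strongest case on the other side has four parts.

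First, within-patient change is not wholly absent: an association with improvement implies that some change score will be derived. That is right, and a reader who infers that no within-patient analysis is intended goes too far. What stands is that this change is neither defined nor tabulated.

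Second, the plan tries to capture patients who stop early by giving them a form at End of Treatment, and the number of observations is reported with every continuous summary (SAP 5.2). So it would be wrong to say that dropouts simply vanish, or that dropout must make quality of life look better. The mitigation is real for each patient, but in cohort 1 the by-visit layout puts that form in a different row. It helps only once it is paired with the same patient's screening score.

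Third, a reader might infer that low-burden patients as a class are left out of the response link. They are not: those with 2-3 units have an RBC-TI value.

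Fourth, the endpoint is exploratory, all summaries are descriptive, the protocol promises only an evaluation of quality of life, and the listings would let anyone derive paired change later. This limits the importance of the point. It does not remove it, because a derivation made later from listings would be post hoc.

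**Conclusion.** The point holds as a low-priority improvement to an exploratory analysis. It does not touch the primary endpoint.

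Two things follow from the text without assumptions. In cohort 1, and in any pooling of the expansion cohorts, the by-visit FACT-An means compare different sets of patients. Patients with 0-1 baseline units have no value in the only planned response association, although mHI-E and HI-E are defined for them.

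The size is not known. The shift of 1 to 9 points at Cycle 5 Day 1, on a total scale of 0 to 188, rests on assumed shares and differences and can go either way. The number of patients with 0-1 units is not in the documents. The stronger conclusion that attrition will produce an apparent benefit is not supported: nothing in the documents says that early discontinuers start with lower scores.

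**What to change.** In SAP section 5.7.3.2:

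1. Reconcile the visit timing with the Appendix 2 schedule and footnotes 18 and 19, including End of Treatment for all cohort 2 and 3 patients and the End of Study form.
2. Add within-patient change from screening, for each subscale and total score, to one named form: Cycle 5 Day 1 for cohort 1 patients who remain on treatment; End of Treatment for early discontinuers and for cohorts 2 and 3. Show it by cohort, since the form falls on different study days. Report change to End of Study separately.
3. For each change, give the number of pairs and the screening mean of patients without a pair.
4. Define improvement from that change, naming the score and any threshold, before database lock.
5. Relate it to mHI-E and HI-E in all expansion patients, and keep RBC-TI for those with at least 2 baseline units.

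The cost is SAP wording and a few exploratory tables from data already collected. Paired change removes the composition shift, but it still describes only patients with a post-screening form. If those without one worsened, it would still look favourable, which is why item 3 is needed.

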5.7.3.3. Subgroup Analyses

Subgroup analyses of the efficacy endpoints will be performed for the following baseline parameters:

- RS mutation status (yes or no),
- Low (< 0.75 mg/kg) vs High (≥ 0.75 mg/kg) Dose Group
- SF3B1 mutation status (yes or no)
- Any splicing factor (yes or no)
- Baseline bone marrow blasts ($< 5\%$ or $\geq 5\%$)
- Baseline erythropoietin (EPO) (≤ 200 or > 200): (≤ 500 or > 500)
- IPSS risk group (low, Int-1, Int-2, or high)
- IPSS-R risk group (low, intermediate, high, very high)

5.8. Safety Analyses

The safety endpoints will be summarized by dose cohort using the Safety Population. The safety endpoints include the incidence of dose-limiting toxicities (DLTs), treatment emergent adverse events, changes in laboratory tests, vital signs and ECG's.

Adverse events will be coded using MedDRA Version 20.0. Severity of AEs will be coded using National Cancer Institute Common Toxicity Criteria for Adverse Events version 5.0 (NCI-CTCAE v5.0).

5.8.1. Dose Limiting Toxicities

A Dose-Limiting Toxicity (DLT) is defined as any of the following toxicities, at any dose level occurring within 28 days of the first administered dose:

- a. Treatment related serious adverse event (SAE) of Grade ≥ 3
- b. Treatment related non-hematologic adverse event (AE) of Grade ≥ 3
- c. Treatment related hematologic AE of Grade ≥ 4

Incidence rates of DLTs will be presented by dose cohort. Details of DLTs will be presented in listings.

5.8.2. Adverse Events

All AEs and SAEs occurring after the Cycle 1 Day 1 dose through 56 days after the last study drug administration are to be reported and documented on the AE CRF.

Treatment emergent adverse events (TEAE) are defined as

1. AE starting or worsening after the first date of study drug;
2. AE occurs on the first date of study drug and the onset check box is marked “Onset after first dose of study drug”;
3. AE with a missing start date and a non-missing stop date on or after the first dose of study drug;
4. AE with both a missing start and stop date.

A drug-related TEAE is defined as any TEAE related to the study medication as assessed by the investigator or with missing assessment of the causal relationship.

The following summaries will also be presented:

- Number and percentage of patients reporting each AE, categorized by System Organ Class (SOC) and Preferred Terms (PT)
- Number and percentage of patients reporting each AE experienced by $\geq 5\%$ and $\geq 10\%$ of patients in all patients by PT
- Number and percentage of patients reporting SAE, categorized by System Organ Class (SOC) and Preferred Terms (PT)
- Number and percentage of patients reporting Grade ≥ 3 AE, categorized by System Organ Class (SOC) and Preferred Terms (PT)
- Number and percentage of patients reporting related AE, categorized by System Organ Class (SOC) and Preferred Terms (PT)
- Number and percentage of patients reporting AE leading to drug withdrawal, categorized by System Organ Class (SOC) and Preferred Terms (PT)
- Number and percentage of AE of interests by cycle: AE of interests include new malignancy and premalignant lesions (excluding benign tumors or benign neoplasia)

Note that counting will be by patient, not event, and patients are only counted once within each SOC or preferred term. If a patient experiences the same AE at more than one severity, or with more than one relationship to study drug, the most severe rating or the stronger causal relationship to study drug will be given precedence. Any missing severity, causality, or outcome will not be imputed and classed as unknown.

All AEs will be listed. The following listings will also be provided: 1) patients with SAEs; 2) patients with Grade ≥ 3 AEs; and 3) patients with AEs leading to discontinuation.

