### 12.2. Dosing Days and Interim Visits

- All screening procedure results required to confirm eligibility must be obtained and reviewed prior to study drug administration. Patient eligibility must be confirmed from these results.
- For any RBC transfusions received during the study, the hemoglobin value just prior to transfusion should be collected.
- A patient will be considered enrolled into the study once a multi-digit patient identification number has been assigned to the patient. After assignment of the patient identification number and the completion of the required procedures, study drug administration may occur. Note that the patient dose must be calculated based on the patient's weight on the day of dosing.
- Negative pregnancy test (urine or serum) is required of female patients of child bearing potential prior to administration of ACE-536 on each dosing day.

- All study procedures on each dosing day must be done prior to administration of study drug.
- For the first dose of ACE-536, dosing should occur after a minimum of 7 days post-transfusion and a minimum of 24 hours prior to a scheduled transfusion. Patients should be observed for a minimum of 30 minutes following treatment with ACE-536.
- If a dose delay is required per the dose modification rules ([Section 10.8.1](#)), the patient will not be dosed. The patient will return weekly for assessment of hematology results and adverse events until the patient is eligible to receive the next dose of ACE-536. The patient should resume the study at the planned dosing cycle (e.g. if the patient missed a dose at C4D1, then they would resume dosing at C4D1 and not skip to C5D1).
- The hematology results can be collected up to 24 hours prior to the dosing day. For Cycle 1 Day 1, the hemoglobin should be available to confirm eligibility within one day prior.
- For dose escalation cohort and expansion cohort 1 patients, a bone marrow aspirate must be performed within 21 days after C3D1 (a bone marrow biopsy is not required). Note: a bone marrow aspirate is not required within 21 days after C3D1 for expansion cohort 2 patients.
- Any non-serious AEs that occur prior to dosing in cycle 1 should be recorded in the Medical History section of the CRF.
- All AEs that occur after dosing in Cycle 1 should be recorded in the AE page of the CRF.

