5.14. Handling of Missing Data and Visit Window

5.14.1. Missing Data

As a general principle, no imputation of missing data for other variables will be done. Exceptions are the start and stop dates of AEs and concomitant medication. The imputed dates will be used to allocate the medication as prior or concomitant medications and to determine whether an AE is/is not treatment emergent. Listings of the AEs and concomitant medications will present the actual partial dates; imputed dates will not be shown.

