5.14.2. Missing Dates for Adverse Event

Imputing partial AE start dates:

- a. If the year is unknown, the date will not be imputed and will be assigned a missing value.
- b. If the month is unknown, then:
 - If the year matches the first dose date, then impute the month and day of the first dose date.
 - Otherwise, assign January.
- c. If the day is unknown, then:
 - If the month and year match the first dose date, then impute the day of the first dose date.
 - Otherwise, assign '01'.

Imputing partial AE stop dates:

- a. If the year is unknown, the date will not be imputed and will be assigned a missing value.
- b. If the month is unknown, then assign December.
- c. If the day is unknown, then assign the last day of the month.

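### An adverse event with a partial start date imputed to the first-dose day is not treatment emergent under the SAP unless it later worsened or the onset box is marked, although an event with no start date is usually counted

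*SAP*

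**What the plan says.** SAP 5.14.1 allows imputation of AE dates and uses the imputed dates to "determine whether an AE is/is not treatment emergent". For a start date with unknown day, SAP 5.14.2 says: "If the month and year match the first dose date, then impute the day of the first dose date". For an unknown month in the same year as first dose, it likewise assigns the month and day of first dose. If the year is unknown, the date stays missing.

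SAP 5.8.2 then gives four ways to be a TEAE:

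- Rule 1: "AE starting or worsening after the first date of study drug".
- Rule 2: "AE occurs on the first date of study drug and the onset check box is marked" to show that onset followed the first dose.
- Rule 3: "AE with a missing start date and a non-missing stop date on or after the first dose of study drug".
- Rule 4: "AE with both a missing start and stop date".

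On what reaches the AE form, Protocol 12.2 says: "All AEs that occur after dosing in Cycle 1 should be recorded in the AE page of the CRF". Protocol 12.2 and 14.5 send non-serious events before the first dose to medical history.

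On causality, SAP 5.8.2 defines a drug-related TEAE to include one whose causality assessment is missing. Further down, the same section says: "Any missing severity, causality, or outcome will not be imputed and classed as unknown".

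**The concern.** The imputation rule and the TEAE definition do not fit together. Imputation places an uncertain onset exactly on the first-dose date. Rule 1 needs a date strictly later than that, and rules 3 and 4 apply only when there is no start date. Rule 2 is then the only way in for an event that did not worsen, and it depends on a check box whose completion for partial dates the documents do not describe.

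An event known to have begun in the month of first dose can therefore be excluded, while one with no known start is included. This ordering has no evident rationale. At stake is a one-directional error in the TEAE endpoint named in SAP 5.8: events missing from the safety summary that more probably than not began after dosing.

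**Working it through.** The documents state no figure on this point, so there is none to reproduce. The check applies the imputation of SAP 5.14.2 and rules 1 to 4 of SAP 5.8.2 literally to each date pattern, for an event not recorded as worsening later. A first-dose date of 15 March 2017 is assumed for illustration.

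| Recorded start | Onset box | Stop date | Start after imputation | TEAE? |
|---|---|---|---|---|
| Day unknown, first-dose month | blank | missing or after first dose | first-dose date | no |
| Day unknown, first-dose month | marked | missing or after first dose | first-dose date | yes, rule 2 |
| Month unknown, first-dose year | blank | missing or after first dose | first-dose date | no |
| Month unknown, first-dose year | marked | missing or after first dose | first-dose date | yes, rule 2 |
| Day unknown, later month | either | missing or after first dose | first of that month | yes, rule 1 |
| Year unknown | either | missing | stays missing | yes, rule 4 |
| Year unknown | either | after first dose | stays missing | yes, rule 3 |

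Rows 1 and 3, set against the last two rows, show the reversal. The choice of first-dose date does not change these classifications.

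**Reach of the gap, box blank and stop date missing**

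- Day unknown: true onset on any of 16 to 31 March, 31 − 15 = 16 days, gives the same recorded value. All 16 of 16 fail.
- Month unknown: with AE collection to Day 169 (Protocol 14.5, 84 days after a last dose on Day 85), there are 169 − 1 = 168 post-dose days, all in the same calendar year in this example. All 168 of 168 fail. With the 56-day collection period in SAP 5.8.2, follow-up ends on Day 85 + 56 = 141, and all 140 post-dose days fail.

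**Effect in one cohort**

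SAP Table 1 gives 3 to 6 patients per escalation cohort, and SAP 5.8.2 counts by patient. If the lost event is a patient's only qualifying occurrence of a preferred term, the incidence falls by 1/6 = 17 to 1/3 = 33 percentage points.

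**Check of the remedy**

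The tested rule counts an event whose partial start date is imputed to the first-dose date unless its stop date is before first dose. The unknown-day loss goes from 16 of 16 to 0 of 16. An event with a stop date of 10 March and a blank box stays non-emergent. A fully dated Day 1 event still follows the box.

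**The case against.** The strongest reply is that the onset box exists to settle uncertain onset. SAP 1 says the plan is to be read with the eCRF, which is not among the documents. If sites complete the box for partial dates, rule 2 recovers the post-dose events and nothing is lost. This stands as a limit on size. It does not repair the rule for a blank box.

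The table bullets in SAP 5.8.2 say AE, not TEAE, and every AE is listed whatever its flag. That also stands. SAP 5.8 names TEAEs as the endpoint, and the drug-related TEAE definition sits just above the bullets, so reading AE as TEAE is natural, but it is not written.

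The AE form need not hold only post-dose events. Only non-serious pre-dose events are diverted to medical history, and Protocol 11.3 requires new malignancies to be reported as serious from consent. So the direction of error is a strong tendency, not a certainty.

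Three stronger readings are tempting, and the documents do not support them:

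- **That DLTs are lost.** SAP 5.8.1 defines a DLT by days from first dose and does not use the TEAE flag. An event imputed to the first-dose date lies inside the 28-day window.
- **That the two causality sentences contradict each other.** They can be read together: the raw value stays unknown, while the definition counts the event as related. The SAP does not say this, so a clarification is useful.
- **That the start-after-stop correction in SAP 5.14.3 must be carried over to AEs.** With the box blank, an event that stopped before first dose is already non-emergent, so the correction changes no flag.

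**Conclusion.** The rule is wrong as written. For an event that did not worsen and whose box is blank, a partial start date imputed to the first-dose date gives non-emergent status, whereas a missing start date gives emergent status unless the stop date is before first dose. The TEAE endpoint of SAP 5.8 certainly loses such an event. The 5.8.2 tables lose it only if AE there means TEAE.

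The total loss cannot be computed from the documents. It depends on how many AE records carry partial dates and on whether the box is completed for them, and neither is given. A reader might divide one month by the roughly 28 weeks of participation to get a share of records. That would mislead, because the 28 weeks include 4 weeks of screening and the first-dose calendar month lies only partly after dosing. The loss is probably small overall. It can still be visible in one escalation cohort, at 17 to 33 percentage points for a preferred term.

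The study is descriptive and has no formal testing, so no inference is at risk. The case for acting is that the error leans toward under-reporting and is cheap to remove.

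**What to change.** Add to SAP 5.8.2: *An AE whose partial start date is imputed to the first-dose date is treatment emergent unless the known date parts, the stop date or the check box show onset before first dose.* Make clear that a blank box alone does not show earlier onset.

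In the same section, state that:

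- the AE summary tables are TEAE tables;
- missing causality counts as related in the related-AE table and is displayed as unknown in the listings.

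The cost is a few SAP sentences before database lock, a small programming change and a slightly higher TEAE count. No new data are needed.
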